#### **3.1. Analysis Sets**

Analysis sets define the subjects to be included in an analysis. Analysis sets and their definitions are provided in this section. The assignment of subjects to analysis sets will be done before the study blind is broken for analysis. The analysis set will be identified and included as a subtitle of each table, figure, and listing.

For each analysis set, the number and percentage of subjects eligible for inclusion will be summarized by treatment group.

A listing of reasons for exclusion from analysis sets will be provided by subject.

##### **3.1.1. All Enrolled Analysis Sets**

All Enrolled Analysis Set includes all subjects who either (a) are randomized into Part A of the study after screening or (b) receive a study subject identification number in Part B of the study after screening.

All Enrolled Analysis Set is the primary analysis set for by-subject listings.

##### **3.1.2. Full Analysis Set**

The Full Analysis Set (FAS) includes all subjects who are randomized/enrolled and receive at least 1 full dose of study drug. This is the primary analysis set for efficacy analyses. Subjects with major eligibility violations that are identifiable based on pre-randomization/enrollment characteristics may be excluded.

### **3.1.3. Safety Analysis Set**

The Safety Analysis Set includes all subjects who are randomized/enrolled and receive at least 1 dose of study drug. This is the primary analysis set for safety analyses.

### **3.1.4. Pharmacokinetic Analysis Set**

The PK Analysis Set will be defined separately for each analyte of interest (ie, LEN, TAF, and its metabolite TFV). Each PK Analysis Set will include all subjects who are randomized/enrolled, receive at least 1 dose of study drug, and have at least 1 nonmissing postdose concentration value reported by the PK laboratory for the respective analyte. This is the primary analysis set for all PK analyses.

### **3.1.5. Peripheral Blood Mononuclear Cell Pharmacokinetic Analysis Set**

The PBMC PK Analysis Set will include all subjects who are enrolled in Part B of the study, receive at least 1 dose of study drug, and have at least 1 nonmissing TFV-DP concentration. The PBMC PK Analysis Set will be used for PK analyses of TFV-DP.

## **3.2. Subject Grouping**

For analyses based on the FAS, subjects will be grouped according to the treatment to which they were randomized/enrolled. For all other analyses, subjects will be grouped according to the actual treatment received. Data from the placebo recipients in Part A of the study will be combined to form one placebo group for the purpose of analysis.

Subjects will be grouped by treatment dose and pooled treatments (all LEN for Part A and all TAF for Part B).

For Part A enrollment, disposition, protocol deviations, demographics, baseline disease characteristics, and HIV-1 RNA < 50 copies/mL by visit tables, an additional total column for all Part A subjects will be included.

For efficacy tables and PK tables, pooled treatment groups will not be included.

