1.2.2.1. GS-US-200-4070 Summary

Study GS-US-200-4070 is an ongoing, Phase 1 study in healthy volunteers evaluating the safety, tolerability, and PK of single ascending doses of a GS-6207 subcutaneous suspension. 40 unique subjects across 4 dosing cohorts have received either SC GS-6207 or placebo (4:1 ratio). Administration of single SC doses of GS-6207 30 mg (Cohort 1), 100 mg (Cohort 2), 300 mg (Cohort 3) and 450 mg (Cohort 4) is complete. PK sampling for Cohorts 1 and 2 (through Day 169 [24 weeks] post dose) is complete and ongoing for Cohorts 3 and 4 (through Day 225 [32 weeks] post dose). Preliminary PK profiles and PK parameters of subcutaneous GS-6207 administered as single doses of 30 mg, 100 mg, 300 mg and 450 mg are presented in [Figure 1-1](#) and [Table 1-1](#) below. Preliminary PK data are available for 168 days post dose for Cohorts 1, 2 and 4, and through 196 days post-dose for Cohort 3.

GS-6207 PK profiles ([Table 1-1](#)) are consistent with sustained delivery. The PK is characterized by prolonged exposure, with measurable concentrations for up to 196 days [28 weeks], to date. The median apparent terminal $t_{1/2}$ is 30-43 days. Increases in GS-6207 mean C_{max} and AUC_{inf} are approximately dose proportional over the dose range of 30-450 mg.

In a preliminary blinded review of the available safety data through February 1, 2019 (n=40), no deaths, serious adverse events (SAEs), or Grade 3-4 adverse events (AEs) have been reported. Injection site reactions occurred in 21 of 40 subjects (53%) these included injection site erythema (15 subjects, 38%), injection site pain (14 subjects, 35%), injection site nodules (9 subjects, 23%), injection site induration (8 subjects, 20%), and injection site swelling (7 subjects, 18%). The only other AE that was reported by more than 10% of subjects was headache (5/40, 13%).

Figure 1-1. Preliminary Mean (SD) GS-6207 Plasma Concentration-Time Profiles Following Single-Dose Administration of Subcutaneous Suspension of GS-6207 30 mg, 100 mg, 300 mg and 450mg (N=8 per cohort)

[figure not shown]

Table 1-1. Study GS-US-200-4070 Preliminary Plasma Pharmacokinetic Parameters of GS-6207 Following Single Dose Administration of Subcutaneous Suspension of GS-6207, 30-450 mg

	Cohort 1 N=8	Cohort 2 N=8	Cohort 3 N=8	Cohort 4 N=8
Dose (Injection Volume)	30 mg (1 x 0.3 mL)	100 mg (1 x 1 mL)	300 mg (3 x 1 mL)	450 mg (3 x 1.5 mL)
PK Parameter Mean (%CV)				

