2. OBJECTIVES

Part A (Cohorts 1 – 5)

The primary objective of this study is as follows:

- To evaluate the short-term antiviral activity of GS-6207 compared to placebo GS-6207, with respect to the maximum reduction of plasma HIV-1 RNA (\log_{10} copies/mL) from Day 1 through Day 10 in HIV-1 infected adult subjects who are antiretroviral treatment naïve or are experienced but capsid inhibitor (CAI) naïve.

The secondary objectives of this study are as follows:

- To investigate the safety and tolerability of GS-6207 as compared to placebo GS-6207 in HIV-1 infected subjects
- To characterize the plasma pharmacokinetics (PK) of GS-6207 in HIV-1 infected subjects
- To characterize the PK/pharmacodynamics of GS-6207 concentration and viral dynamics of HIV-1.
- To determine the number and percentage of subjects ever achieving HIV-1 RNA < 50 copies/mL by Day 10 at each dose level
- To examine any emergence of capsid inhibitor (CAI) resistance

Part B (Cohorts 6 – 8)

The primary objective of this study is as follows:

- To evaluate the short-term antiviral activity of TAF with respect to the maximum reduction of plasma HIV-1 RNA (\log_{10} copies/mL) from Day 1 through Day 10 in HIV-1 infected adult subjects who are antiretroviral treatment naïve or are experienced but without resistance to TAF.

The secondary objectives of this study are as follows:

- To investigate the safety and tolerability of TAF in HIV-1 infected subjects
- To characterize the pharmacokinetics (PK) of TAF and its metabolites in HIV-1 infected subjects
- To examine any emergence of TAF resistance.

CCI

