### 1.1. Study Objectives

#### **Part A (LEN Cohorts 1-5)**

The primary objective of this study is as follows:

- To evaluate the short-term antiviral activity of LEN compared to placebo LEN, with respect to the maximum reduction of plasma HIV-1 RNA ( $\log_{10}$  copies/mL) from Day 1 through Day 10 in HIV-1 infected adult subjects who are antiretroviral treatment (ART) naïve or are experienced but capsid inhibitor (CAI) naïve

The secondary objectives of this study are as follows:

- To investigate the safety and tolerability of LEN as compared to placebo LEN in HIV-1 infected subjects
- To characterize the plasma pharmacokinetics (PK) of LEN in HIV-1 infected subjects
- To characterize the PK/pharmacodynamics (PK/PD) relationship between LEN concentration and the viral dynamics of HIV-1
- To determine the number and percentage of subjects ever achieving HIV-1 RNA < 50 copies/mL by Day 10 at each dose level
- To examine any emergence of CAI resistance

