### Treatment Groups and Dosing

#### **Part A:**

Subjects will be randomized centrally within a cohort in a 3:1 ratio to receive active LEN (n = 6) or placebo (n = 2). A single dose of LEN or placebo will be administered as a subcutaneous (SC) injectable free acid suspension in the morning without regard to food. LEN doses may be administered as multiple SC injections at different abdominal sites. The doses to be evaluated in Cohorts 2 through 5 will be determined based on cumulative safety (through at least Day 14), available PK, and viral kinetic data from previous cohorts, as well as available safety (through at least Day 14) and PK data from Study GS-US-200-4070 (Phase 1, first-in-human, single ascending dose study of GS-6207 SC suspension formulation, in which GS-6207 30 to 450 mg was administered subcutaneously). As such, Cohorts 2-5 may be initiated in parallel. Selected doses will be either lower than, or no more than 3-fold higher than, previously evaluated doses either in this study or in Study GS-US-200-4070. The Sponsor may elect to hold dosing or stop study enrollment at any time based on review of preliminary safety and PK data. The protocol prespecified doses and the corresponding number of injections for each cohort are provided below.

Cohort	Protocol Prespecified Dose of LEN or Placebo	Number of Injections
1	150 mg	1
2	50 mg	1
3	450 mg	3
4	20 mg	1
5	750 mg	5

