### **1.3. Sample Size and Power**

#### **Part A**

A sample size of 6 subjects in each LEN treatment group and a total of 10 placebo subjects from all cohorts combined will provide 99% power to detect a treatment difference of 2.79  $\log_{10}$  copies/mL in maximum reduction of HIV-1 RNA between at least one of the LEN treatment groups and the placebo group. In this power analysis, it is assumed that a common standard deviation (SD) for maximum reduction in HIV-1 RNA is 0.526  $\log_{10}$  copies/mL (based on Study GS-US-141-1219) and a 2-sided t-test is conducted at an alpha level of 0.05.

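### For injection site reactions, pooled placebo mixes 1, 3 and 5 injections, so each dose-versus-placebo reading is confounded with number of injections (minor)

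*SAP*

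**What the plan says.** Part A has a secondary objective on tolerability against placebo (Protocol section 2): "To investigate the safety and tolerability of GS-6207 as compared to placebo GS-6207 in HIV-1 infected subjects".

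SAP section 1.2 randomises six active and two placebo subjects within each of five cohorts and tabulates the injections per cohort: 1 for 150, 50 and 20 mg, 3 for 450 mg and 5 for 750 mg. The dose column is headed "Protocol Prespecified Dose of LEN or Placebo", so placebo recipients get their cohort's number of injections. The sample size text (SAP 1.3) counts "a total of 10 placebo subjects from all cohorts combined".

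SAP 3.2 then sets the grouping: "Data from the placebo recipients in Part A of the study will be combined to form one placebo group for the purpose of analysis". Columns are the individual doses plus an all-LEN column; only efficacy and PK tables drop the latter. SAP 7.1.6 summarises treatment-emergent adverse events by treatment group. SAP 3.3 uses no covariates and 3.4 no subgroups. The visible text has no injection-site summary by number of injections.

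**The concern.** Pooling placebo across cohorts is natural for viral load, where number of injections should not matter. A local reaction is different: each further injection may be a further chance to react. Injection site reactions were the leading event in the healthy-volunteer study of the same suspension (21 of 40 subjects, 53%; Protocol 1.2.2.1), and the placebo is itself an injected vehicle with the same listed excipients (Protocol 5.2.1.1).

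In Part A, number of injections rises with dose. Placebo from the same cohort is what separates drug from procedure, and the trial randomised that control. The pooled column gives it up at dose level: no dose group has the placebo group's mix of injections. A reader who subtracts the placebo column from a dose column may credit to the drug what belongs to the number of injections. At the low doses the same reader may miss a real local effect, because the comparator had more injections on average.

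**Working it through.** **Inputs.** Injections per cohort and 6:2 allocation: SAP 1.2. Pooling rule: SAP 3.2. The documents give no placebo reaction rate per injection. The 53% comes from a blinded review of 32 active and 8 placebo subjects (Protocol 1.2.2.1 and 1.5.1), and all 21 reactors could have been on active drug. The per-injection risk p is therefore an assumption and is shown over a range.

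**Plan's own figure.** Placebo n = 5 cohorts × 2 = 10, as SAP 1.3 states. The plan gives no figure for injection-site tolerability.

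**Mix of injections (planned numbers).**
- Placebo: 3 × 2 = 6 with one, 2 with three, 2 with five, so 60/20/20%. Mean = (6×1 + 2×3 + 2×5)/10 = 2.2.
- All-LEN: 3 × 6 = 18 with one, 6 with three, 6 with five, so again 60/20/20%. Mean = (18×1 + 6×3 + 6×5)/30 = 2.2.
- Each dose column: everyone has 1, or 3, or 5.

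**Model with no drug effect and independent injections.** A subject with k injections reacts with probability r_k = 1 − (1 − p)^k. Pooled placebo = 0.6 r_1 + 0.2 r_3 + 0.2 r_5. The artefact is r_k minus pooled placebo.

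Example at p = 0.20: r_1 = 0.200, r_3 = 1 − 0.8³ = 0.488, r_5 = 1 − 0.8⁵ = 0.672. Pooled = 0.120 + 0.098 + 0.134 = 0.352.

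| p | r_1 | r_3 | r_5 | Pooled placebo | Artefact at 20/50/150 mg | Artefact at 450 mg | Artefact at 750 mg |
|---|---|---|---|---|---|---|---|
| 0.05 | 5.0% | 14.3% | 22.6% | 10.4% | −5.4 | +3.9 | +12.2 |
| 0.10 | 10.0% | 27.1% | 41.0% | 19.6% | −9.6 | +7.5 | +21.3 |
| 0.20 | 20.0% | 48.8% | 67.2% | 35.2% | −15.2 | +13.6 | +32.0 |

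Artefacts are in percentage points. For all-LEN the artefact is 0 at every p, because the mix is the same.

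**Which directions are robust.**
- One injection: r_1 − pooled = −0.2(r_3 − r_1) − 0.2(r_5 − r_1). This is negative whenever risk rises with number of injections.
- Five injections: r_5 − pooled = 0.6(r_5 − r_1) + 0.2(r_5 − r_3). This is positive under the same condition.
- Three injections: r_3 − pooled = 0.6(r_3 − r_1) − 0.2(r_5 − r_3). This is positive only if the rise from 3 to 5 is less than three times the rise from 1 to 3. Independence guarantees that, since the ratio of the two rises is (1 − p)², which is below 1. Monotonicity alone does not.

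**Other extreme.** If a person reacts to every injection or to none, r_1 = r_3 = r_5 and every artefact is 0.

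**The case against.** The strongest reply is that the plan already contains the comparison its objective needs. The tolerability objective is against placebo and does not mention dose, whereas the neighbouring objective on HIV-1 RNA below 50 copies/mL asks for results at each dose level. The all-LEN column is balanced with pooled placebo for number of injections. No test or difference is specified for adverse events, so there is no type I error to protect. Adverse events and exposure are also listed by subject. All of this stands, and it limits the point to informal dose-versus-placebo readings of a descriptive table.

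The size is also open. It depends on an unknown placebo rate per injection and on independence between injections in one person. That stands too, so the effect is one that could occur, not one that will.

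A reader might go further and infer that pooling builds a false dose-response into the data used to choose doses. The documents do not support that. The dose columns read the same (20%, 49% and 67% in the example) whatever placebo column stands beside them, and the rise truly describes each regimen as given. Pooling distorts only how much of it is attributed to drug. Dose selection under Protocol 8.9 rests on interim unblinded reviews under a charter, and nothing visible says those reviews use the SAP 7.1.6 tables.

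What the reply does not remove is that the dose columns will be printed beside a placebo column that matches none of them on number of injections, and nothing in the plan warns of it.

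**Conclusion.** The point holds as a minor one. If reaction risk rises with number of injections, dose-level contrasts with pooled placebo for injection site reactions are confounded with that number. In expectation, drug-attributable reactions could be overstated at 750 mg and understated or hidden at 20, 50 and 150 mg. Overstatement at 450 mg needs the further condition shown above, which the independent-injection model meets.

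Under that model with no drug effect, the artefact at 750 mg and at the one-injection doses runs from about +12/−5 points at 5% per injection to +32/−15 at 20%. Dependence within a subject pulls it towards zero. Group sizes are the planned ones. All-LEN versus pooled placebo, the primary efficacy analysis and its power are not affected.

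**What to change.** Keep the pooled placebo column. Add to SAP 7.1.6 one descriptive table of injection site reactions by number of injections, listing the preferred terms counted:

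- 1 injection: 18 LEN vs 6 placebo, with 20, 50 and 150 mg shown within it. Volume differs there: 0.2, 0.5 and 1.5 mL at 100 mg/mL.
- 3 injections: 6 LEN (450 mg) vs 2 placebo.
- 5 injections: 6 LEN (750 mg) vs 2 placebo.

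Do not merge the last two rows to gain numbers. At p = 0.20 the merged placebo rate would be (48.8 + 67.2)/2 = 58.0%, which leaves artefacts of about +9 points at 750 mg and −9 at 450 mg.

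Footnote the adverse event tables: for these events, dose-level contrasts with pooled placebo are confounded with number of injections, and all-LEN versus pooled placebo is the balanced unstratified comparison.

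The cost is one table from data already collected. The drawback is sparse placebo cells of 6, 2 and 2. With no reactor among 2, the exact 95% upper limit is 1 − 0.025^(1/2) = 84%; with none among 6 it is 1 − 0.025^(1/6) = 46%. The table should be labelled descriptive only.

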## **3.3. Strata and Covariates**

This study does not use a stratified randomization schedule when enrolling subjects. No covariates will be included in the analyses.

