### **5.2. Other Baseline Characteristics**

Other baseline characteristics include HIV-1 RNA (log10 copies/mL), CD4 cell count (/μL), CD4 percentage (%), mode of infection (HIV risk factors), HIV disease status, ever participated in pre-exposure prophylaxis (Yes/No), ever participated in post-exposure prophylaxis (Yes/No), and ART status (experienced/naïve). These baseline characteristics will be summarized by treatment group and overall using descriptive statistics for continuous variables and using number and percentage of subjects for categorical variables. The summary of these baseline characteristics will be provided for the Safety Analysis Set. No formal statistical testing is planned.

A by-subject listing of other baseline characteristics will be provided by subject ID number in ascending order.

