## **6. EFFICACY ANALYSES**

### **6.1. Primary Efficacy Endpoint**

The primary efficacy endpoint is the maximum reduction of plasma HIV-1 RNA ( $\log_{10}$  copies/mL) from Day 1 through Day 10.

Data from the placebo recipients in Cohorts 1-5 will be combined to form one placebo group. Each of the LEN treatment groups will be compared to the pooled placebo group with respect to the primary efficacy endpoint using the 2-sided t-test conducted at an alpha level of 0.05. Pairwise comparison of the maximum reduction of plasma HIV-1 RNA ( $\log_{10}$  copies/mL) from Day 1 through Day 10 among all LEN treatment groups will also be performed. The analysis will be conducted using the FAS.

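### The primary analysis bars covariates and tests doses with separate two-sample t-tests; one ANCOVA on baseline HIV-1 RNA over all Part A arms would modestly tighten the dose estimates at little cost

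*SAP*

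**What the plan says.** SAP 3.3 notes that randomization is not stratified and adds: "No covariates will be included in the analyses". For the primary endpoint, the largest fall in log10 HIV-1 RNA between Day 1 and Day 10, SAP 6.1 states: "Data from the placebo recipients in Cohorts 1-5 will be combined to form one placebo group". Each LEN dose is compared with that group "using the 2-sided t-test conducted at an alpha level of 0.05", and pairwise comparisons "among all LEN treatment groups will also be performed". SAP 6.3.2 uses the same method for change from baseline at each visit through Day 10. Protocol 8.5.1 names the same t-test.

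Baseline HIV-1 RNA is available. SAP 5.2 says: "Other baseline characteristics include HIV-1 RNA"; it is summarised by treatment group and listed by subject. Its only role in the efficacy analysis is as the value subtracted to form the endpoint. Neither document gives an ANOVA, an ANCOVA or a variance pooled over all arms for the primary endpoint, and the SAP does not say whether its t-tests use pooled or Welch variance.

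**The concern.** The endpoint is a change in a quantity whose starting value varies widely and is measured before dosing. Entry runs from 5,000 to 400,000 copies/mL (SAP 1.2), which is 1.9 log10. The starting value also limits what can be observed: under the rule in protocol 8.3 and SAP 3.7 that a result reported as below 20 is set to 19, the largest measurable fall is log10(5,000/19) = 2.42 from the bottom of the range and log10(400,000/19) = 4.32 from the top.

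With 6 subjects per dose, two features of the plan cost precision. Each t-test takes its SD from two small arms although six arms are available, and any relation between baseline and response stays in the error term. According to protocol 1.4.1 the data will support dose selection for Phase 2 and 3, so the width of the dose estimates matters more here than whether active differs from placebo.

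**Working it through.** **Inputs.** SAP 1.3, Part A: "A sample size of 6 subjects in each LEN treatment group and a total of 10 placebo subjects from all cohorts combined"; common SD 0.526; two-sided alpha 0.05. That is 5 × 6 + 10 = 40 subjects. The within-arm correlation of baseline HIV-1 RNA with the maximum reduction (rho) is in neither document; values of 0, 0.3 and 0.5 are assumed.

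**The plan's own figure.** The SAP says the sample size "will provide 99% power to detect a treatment difference of 2.79" log10 copies/mL. SE = 0.526 × √(1/6 + 1/10) = 0.272, so the noncentrality is 2.79/0.272 = 10.3 on 14 df and power is above 99.99%. The claim holds with room to spare: 99% power is reached at a difference of about 1.26.

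**Two-sample t-tests.** Half-width = t × SE.
- LEN vs placebo, df 6 + 10 − 2 = 14: 2.145 × 0.272 = 0.583.
- LEN vs LEN, df 6 + 6 − 2 = 10: SE = 0.526 × √(2/6) = 0.304; 2.228 × 0.304 = 0.677.

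**One model over six arms.** ANOVA without the covariate has 40 − 6 = 34 df (t = 2.032). ANCOVA has 33 df (t = 2.035), and its SE is multiplied by √(1 − rho²) × √(1 + 1/32), where the second factor is the expected cost of imbalance in the covariate.

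| 95% CI half-width | t-test | ANOVA | ANCOVA, rho 0 | rho 0.3 | rho 0.5 |
|---|---|---|---|---|---|
| LEN vs placebo | 0.583 | 0.552 | 0.561 | 0.535 | 0.486 |
| LEN vs LEN | 0.677 | 0.617 | 0.627 | 0.599 | 0.543 |

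Relative to the t-test, ANCOVA is narrower by 4%, 8% and 17% (LEN vs placebo) and by 7%, 11% and 20% (LEN vs LEN). At rho 0 the whole gain comes from error df. The covariate improves on plain ANOVA only when |rho| exceeds about 0.18.

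**Effect on the estimate itself.** The SE for LEN vs placebo moves from 0.272 to 0.276, 0.263 or 0.239 at rho 0, 0.3 or 0.5; for LEN vs LEN, from 0.304 to 0.308, 0.294 or 0.267. The reduction at rho 0.3 to 0.5 is therefore about 0.01 to 0.04 log10.

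**Simulation.** With a common SD, mean half-widths for LEN vs placebo were 0.571 by t-test and 0.529 by ANCOVA at rho 0.3, and 0.573 and 0.483 at rho 0.5, all with about 95% coverage. The gain is an average: ANCOVA was narrower in 58% of trials at rho 0 and 83% at rho 0.5.

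**If placebo is less variable.** With placebo SD 0.2 (assumed) and rho 0.3, a pooled-variance t-test gives 0.38 but covers only about 88 to 89%, and Welch gives 0.53 with 95%. ANCOVA with one residual variance gives 0.47 for LEN vs placebo, but its LEN-vs-LEN intervals cover only about 92%. ANCOVA with a separate placebo variance gives 0.45 for LEN vs placebo with 95% coverage, and about 0.61 for LEN vs LEN against 0.66 by t-test, also with about 95%. When the SDs are in fact equal the separate variance costs almost nothing (0.532 and 0.482 at rho 0.3 and 0.5).

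**The case against.** The strongest reply is that this is a refinement to a proof-of-concept study whose primary conclusion is not in doubt. That is right about power, and the point claims nothing there.

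Several stronger readings are tempting, and the documents do not support them:
- A reader might infer that the plan ignores baseline HIV-1 RNA. It does not: the endpoint subtracts it, and SAP 5.2 displays it by group, so an imbalance would be visible.
- A reader might take chance imbalance to add a large avoidable error. Suppose baseline were spread evenly over the entry range (SD 0.55). Imbalance between 6 and 10 subjects then has SE 0.55 × 0.516 = 0.28, and an assumed slope of 0.3 to 0.5 makes that 0.09 to 0.14 log10. But these components sit in quadrature inside the existing SE of 0.272. Removing them leaves about 0.26 or 0.24.
- A reader might infer that these estimates alone choose the later dose. Protocol 8.9 bases that choice on safety, viral kinetics and PK together, and allows it at an interim review.

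The sharpest technical objection is that the assay floor can act only where virus falls a long way, so a slope may exist in the LEN arms and not in placebo. This stands in part. In simulation with slope 0.3 in LEN arms only, the LEN-vs-placebo estimate was no more stable (sampling SD 0.275 against 0.274). Intervals were still narrower on average: about 0.54 or 0.51 against 0.57 at slopes of 0.3 or 0.5, with coverage of about 94 to 95%. The floor may also bind rarely: the Cohort 1 Day 10 falls in protocol 1.2.2.4 ran from 1.49 to 2.06, short of 2.42, although higher doses could go further. The common slope therefore needs checking.

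**Conclusion.** The point holds as an improvement that should be made. It is not an error in the plan. Under the SAP's common SD, one ANCOVA gives expected intervals 4 to 17% narrower for LEN vs placebo and 7 to 20% narrower for LEN vs LEN over rho 0 to 0.5.

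Part of that is only pooling of error df. The rest depends on a correlation that the documents do not give, and protection against chance imbalance exists only if baseline is prognostic. The figures also take the t-tests to use two arms at a time, which is the plain reading and not stated text.

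It would be wrong to infer that adjustment makes the LEN-vs-LEN contrasts randomized comparisons. Randomization is within cohort (SAP 1.2) and each dose is its own cohort; adjusting for baseline HIV-1 RNA removes one difference between cohorts and leaves the others.

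**What to change.** In SAP 3.3, 6.1 and 6.3.2:
- Specify an ANCOVA of maximum reduction on treatment (five LEN doses plus pooled placebo) and baseline log10 HIV-1 RNA, with all Part A subjects in one model. Use the same form for the by-visit changes through Day 10.
- Allow a separate residual variance for placebo.
- Report adjusted differences with 95% CIs.
- Prespecify a check of the common slope between placebo and LEN arms.
- Keep the protocol 8.5.1 t-test as a sensitivity analysis, stating whether its variance is pooled or Welch.
- Record the change from protocol 8.5.1 in SAP 6.4. SAP 2.1 says some sponsor staff saw unblinded interim data, so give the date and reason.

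The cost is SAP wording, minor programming, one degree of freedom, the assumption of a linear common slope, and a documented departure from the protocol's stated test. No new data, visits or subjects are needed.
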